8.1.2 Adverse Event Relationship to Study Treatment or Procedure

The relationship of an AE to the study treatment or procedure should be based on the judgment of the investigator and assessed using the following the guidelines:

- Definitely: Previously known toxicity of study treatment or procedure; or an event that follows a reasonable temporal sequence from administration of the study treatment or procedure; that follows a known or expected response pattern to the suspected study treatment or procedure; that is confirmed by stopping or reducing the dosage of the study treatment or procedure; and that is not explained by any other reasonable hypothesis.
- Probably: An event that follows a reasonable temporal sequence from administration of the study treatment or procedure; that follows a known or expected response pattern to the suspected study treatment or procedure; that is confirmed by stopping or reducing the dosage of the study treatment or procedure; and that is unlikely to be explained by the known characteristics of the subject's clinical state or by other interventions.
- Possibly: An event that follows a reasonable temporal sequence from administration of the study treatment or procedure; that follows a known or expected response pattern to

that suspected of study treatment or procedure; but that could readily have been produced by a number of other factors.

 Unrelated: An event that can be determined with certainty to have no relationship to the study treatment or procedure.

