Appendix F: Serious Adverse Event Reporting Form

Nasa	ocol Title: A Feasibility Study Evaluating a Novel Mask (Nasal Reservoir Cannula) Plus Standard al Cannula vs Standard Nasal Cannula Alone for Supplemental Oxygen Delivery in the Treatment of pitalized Pediatric Patients with Hypoxemia Due to Severe Pneumonia
	Pt_IP number: Study ID number:
1.	SAE Onset Date: (dd/mm/yyyy)
2.	SAE Stop Date:(dd/mm/yyyy)
3.	Location of serious adverse event:
4.	Was this an unexpected adverse event? Yes No
5.	Brief description of participant(s) with no personal identifiers: Sex: F M Age:
6.	Brief description of the nature of the serious adverse event (attach description if more space needed):
7.	Category of the serious adverse event:
	☐ death – date//(dd/mmm/yyyy) ☐ congenital anomaly / birth defect ☐ life-threatening ☐ required intervention to prevent ☐ hospitalization-initial or prolonged permanent impairment ☐ disability / incapacity ☐ other:
8.	Intervention type:
	Medication or Nutritional Supplement: specify
	Device: Specify:
	Surgery: Specify:
	Behavioral/Life Style: Specify:

9.	Relationship of event to intervention:
	Unrelated (clearly not related to the intervention) Possible (may be related to intervention) Definite (clearly related to intervention)
10.	Was study intervention discontinued due to event? Yes No
11.	What medications or other steps were taken to treat serious adverse event?
12.	List any relevant tests, laboratory data, history, including preexisting medical conditions
13.	Type of report:
	☐ Initial ☐ Follow-up ☐ Final
	Signature of Principal Investigator: Date:

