APPENDIX H Data and Safety Monitoring Plan

A. Confidentiality

- 1. Protection of Subject Privacy— During this study, a physical examination and blood tests will be performed. Data will be kept in strict confidence. No information will be given to anyone without permission from the parents of the participant. This statement guarantees confidentiality. Confidentiality is assured by use of study identification numbers. All clinical and laboratory data will be identified only by the study identification number unique to the subject. No participant specimens will be stored for future use.
- 2. Database Protection— The database is secured with password protection. The informatics manager receives only coded information, which is entered into the database under those identification codes. Electronic communication with outside collaborators involves only unidentifiable information.
- 3. Confidentiality during Adverse Event Reporting— Adverse event reports will not include subject-identifiable material. Each will include the study identification number only.

B. Adverse Event Information

1. Definitions- An adverse event (AE) will be defined as **any** new unfavorable or unintended sign, symptom, or disease or change of an existing condition, which occurs during or within 1 hour after treatment, whether or not considered treatment-related. If clinically significant laboratory values lead to or are associated with clinical symptom(s), the diagnosis should be reported as an AE. Lack of treatment effect is not an adverse event in clinical trials because the purpose of the clinical trial is to establish (or evaluate for) a treatment effect.

A serious adverse event (SAE) is defined as an AE that suggests a significant hazard or side effect, regardless of the relationship to study treatment. An SAE includes, but may not be limited to, any event that:

- Results in death.
- Is life-threatening. This definition implies that the subject, in the view of the investigator, is at immediate risk of death from the event. It does not include an event that, had it occurred in a more serious form, might have caused death.
- Requires inpatient hospitalization or prolongs existing hospitalization.
- Results in persistent or significant disability/incapacity.
- 2. Classification of AE Severity AEs will be labeled according to severity, which is based on their impact on the patient, per this Event Grading Scale:

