 - Grade 1 Mild: Transient of mild discomfort; no limitation in activity; no medical intervention/therapy required.
 - Grade 2 Moderate: Mild to moderate limitation in activity some assistance may be needed; no medical intervention/therapy required.

- Grade 3 Severe: Marked limitation in activity, some assistance usually required; medical intervention/therapy required, hospitalizations possible.
- Grade 4 Life-threatening: Extreme limitation in activity, significant medical intervention/therapy required.
- 3. AE Attribution Scale— AEs will be categorized according to the likelihood that they are related to the study intervention. The relationship of an AE/SAE to the study treatment or procedure should be based on the judgment of the investigator and assessed using the following the guidelines:
 - Definitely: Previously known toxicity of study treatment or procedure; or an event that follows a reasonable temporal sequence from administration of the study treatment or procedure; that follows a known or expected response pattern to the suspected study treatment or procedure; that is confirmed by stopping or reducing the dosage of the study treatment or procedure; and that is not explained by any other reasonable hypothesis.
 - Probably: An event that follows a reasonable temporal sequence from administration of the study treatment or procedure; that follows a known or expected response pattern to the suspected study treatment or procedure; that is confirmed by stopping or reducing the dosage of the study treatment or procedure; and that is unlikely to be explained by the known characteristics of the subject's clinical state or by other interventions.
 - Possibly: An event that follows a reasonable temporal sequence from administration of the study treatment or procedure; that follows a known or expected response pattern to that suspected of study treatment or procedure; but that could readily have been produced by a number of other factors.
 - Unrelated: An event that can be determined with certainty to have no relationship to the study treatment or procedure.
- 4. Expected Risks— Expected risks to the subjects are mild discomfort due to blood draws. These risks are considered to be minimal and are addressed in the protocol and consent form. There is minimal risk associated with the device.

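### The causality scale has no grade for a plausible but unexpected event, and the SAE form neither matches the scale nor records a time of onset

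*Protocol*

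**What the plan says.** Section 8.1.2 of the protocol, repeated in Appendix H B.3, grades causality in four steps.

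- *Definitely* has two routes. One begins "Definitely: Previously known toxicity of study treatment or procedure". The other combines timing, a response pattern, confirmation on stopping or reducing, and no other reasonable explanation.
- *Probably* needs plausible timing, an event "that follows a known or expected response pattern to the suspected study treatment or procedure", confirmation on stopping or reducing, and an unlikely alternative cause.
- *Possibly* reads "Possibly: An event that follows a reasonable temporal sequence from administration of the study treatment or procedure; that follows a known or expected response pattern", and allows that other factors could readily have produced the event.
- *Unrelated* is "An event that can be determined with certainty to have no relationship to the study treatment or procedure".

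Section 8.1.1 requires every AE to be classified for causality. Section 10.5.6 tabulates treatment-related AEs as well as all AEs, by treatment group.

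On what is known of the device, section 2.3 reports breathing-simulator experiments, and Appendix H B.4 states: "Expected risks to the subjects are mild discomfort due to blood draws".

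The SAE form in Appendix F offers these relationship options: "Unrelated (clearly not related to the intervention) Possible (may be related to intervention) Definite (clearly related to intervention". Its onset field is "SAE Onset Date: (dd/mm/yyyy", and the stop field has the same date format. Appendix H B.1 limits AEs to those "which occurs during or within 1 hour after treatment".

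**The concern.** A first clinical feasibility study of a device should be able to record effects that nobody predicted. A scale that accepts an event as related only if it fits a pattern already known or expected leaves the unpredicted event without a grade. The investigator must then either stretch the definition or choose *Unrelated* without the certainty it demands.

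The form adds a second difficulty. It uses a different scale from the protocol, so the same event can carry two different grades depending on the source. Each child also uses both interfaces within about 2 hours, so a calendar date does not show which one was in use when the event began.

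At stake are the consistency of the treatment-related AE tables and the ability to attribute events to the mask or the cannula. Preliminary safety information of this kind is part of the study's primary objective (section 3).

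**Working it through.** There is no planned figure to reproduce. The check sets the definitions, the form and the schedule side by side.

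**1. Does every event have a grade?** Take an event that begins while the mask is on, fits no known or expected pattern, and cannot be ruled out with certainty.

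| Grade (8.1.2, Appendix H B.3) | Condition that decides | Met? |
|---|---|---|
| *Definitely*, route 1 | previously known toxicity | No |
| *Definitely*, route 2 | known or expected pattern | No |
| *Probably* | known or expected pattern | No |
| *Possibly* | known or expected pattern | No |
| *Unrelated* | certainty of no relationship | No |

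The conditions within a grade (or route) are cumulative, so failing one is enough. None of the four grades fits.

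**2. Is this a realistic case here?** Section 2.3 supports the device with simulator data only. Appendix H B.4 names blood-draw discomfort as the expected risk and no device reaction. A pattern could be argued from mechanism, because 2.3 says the device works by increasing dead space. Appendix H B.4, however, declares hypercapnia, the need for ventilation and pneumothorax to be independent of the device, which pulls against that argument.

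**3. Does the form match the scale?** The scale has four grades and the form has three: 4 − 3 = 1 missing, namely *Probably*. An event graded *Probably* under 8.1.2 has to be moved up or down on the form. The form's *Possible* also carries no pattern condition. The event in step 1 can therefore be ticked *Possible* on the form while having no grade under 8.1.2. The relationship summaries in 10.5.6 would depend on which source is used.

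**4. Can the form's structured fields place the event in time?** Period 1 lasts 1 h and Period 2 lasts 1 h, so 1 + 1 = 2 h. With the 1-hour window in Appendix H B.1, 2 + 1 = 3 h. This gives three consecutive 1-hour intervals: one on the mask, one on the cannula (order set by randomisation), and the hour after. A date separates none of them unless midnight happens to fall between two. The form has no field for study period or for the interface in use at onset.

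**5. Which rules need that information?**
- *Definitely* (route 2) and *Probably* require confirmation on stopping or reducing. Date-only onset and stop fields cannot show whether an event resolved when the mask came off.
- Appendix H B.1 counts events up to 1 hour after treatment, while 10.5.6 calls an AE treatment-emergent only until treatment is completed. Separating the two needs a time.
- A comparison of devices in a crossover needs the exposure at onset.

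**The case against.** The strongest reply is that nothing is lost in practice, and much of it stands.

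- **Reporting does not depend on the grade.** Section 8.1.3 sends any SAE to the sponsor within 24 hours and defines SAEs without regard to relationship. Appendix H B.5 lists unanticipated events as a trigger alongside possibly related ones. All AEs are recorded whatever their causality, and 10.5.6 tabulates all of them as well as the treatment-related ones.
- **The form can hold an unexpected event.** Its *Possible* and *Definite* options carry no pattern condition. Item 4 asks whether the event was unexpected. There is also a free-text narrative, a line for the device and an item on discontinuation.
- **The period can be found elsewhere.** The synopsis and Appendix A schedule AE recording separately in Period 1 and Period 2, and the randomised sequence then gives the interface. The Period 2 list in 4.2.2.2 omits AE recording, which weakens this back-up without removing it.
- **The scale is guidance.** Section 8.1.2 leaves the assessment to the investigator's judgment, and an expectation may be formed from the mechanism.

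A reader might infer that an SAE caused by the device can be neither classified nor tied to the mask hour. The documents do not support that, for the reasons above. Other case report form pages are also not shown, so it cannot be said that the study collects no onset time.

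The reply does not remove the gap in the written definitions or the conflict between scale and form. That the form accepts an event the scale cannot grade is itself the inconsistency.

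**Conclusion.** The point holds in a limited form. As written, 0 of 4 grades fit an event that is plausible in time, unexpected and not excluded with certainty. The SAE form lacks 1 of the 4 grades. Its date fields normally distinguish 0 of the 3 one-hour intervals.

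The effect is on consistent grading and on device attribution in the treatment-related AE tables of 10.5.6. SAE reporting is unaffected. With up to 20 children and descriptive summaries, no formal test depends on this, and the documents give no basis for estimating how many events would be affected.

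The conclusion assumes that the definitions are applied as written. The timing point concerns the SAE form alone and makes no claim about case report form pages that are not shown. The correction should be made, because the scale and the form are fixed in this protocol and the change is small.

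**What to change.** 1. In 8.1.2 and Appendix H B.3, remove the pattern condition from *Possibly*. Define the grade as plausible timing where a contribution of the study treatment or procedure cannot be excluded.
2. In Appendix F, use the same four grades, with the same definitions.
3. In Appendix F, add clock time to the onset and stop fields, and add fields for study period and for the interface in use at onset.

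The cost is a wording change in two places and a few fields on one form. The downside is that slightly more events may be classed as possibly related.

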8.1.3 Serious Adverse Event Definition and Reporting Procedures

For purposes of this trial, a serious adverse event (SAE) is defined as an AE that suggests a significant hazard or side effect, regardless of the relationship to study treatment. An SAE includes, but may not be limited to, any event that:

- Results in death.
- Is life-threatening. This definition implies that the subject, in the view of the investigator, is at immediate risk of death from the event. It does not include an event that, had it occurred in a more serious form, might have caused death.
- Requires inpatient hospitalization or prolongs existing hospitalization.
- Results in persistent or significant disability/incapacity.

Any SAE that meets the above definition and occurs in a subject during the course of the study must be reported to the sponsor by telephone within 24 hours of the investigator becoming aware of the event. In addition, a SAE reporting form must be completed by the investigator and faxed to the study sponsor within 24 hours of the investigator becoming aware of the event. In addition, the site investigator must report SAEs to their local Institutional Review Board/Institutional Ethics Committee (IRB/IEC) in accordance with the IRB/IEC's standard operating procedures and policies.

Medical and scientific judgment will be exercised in deciding whether classification of an adverse event as serious is appropriate in other situations, such as important medical events that may not be immediately life-threatening or result in death or hospitalization, but may jeopardize the subject or require intervention to prevent one of the outcomes listed in the definition above. These should also usually be considered serious. Examples of such events include allergic bronchospasm requiring intensive treatment in an emergency room or at home, blood dyscrasias or convulsions that do not result in inpatient hospitalization, or the development of drug dependence or abuse.

Please refer to the Data and Safety Monitoring Plan (Appendix H) for further details, including stopping rules.

8.1.4 Laboratory Tests

Clinical laboratory tests will be performed at the times specified in the Study Schedule (see Appendix A) and will follow the local and regular protocol for patients with respiratory distress. All clinical laboratory assessments will be analyzed at the participating site's local laboratory. Clinically significant laboratory abnormalities (see Appendix F), which

are new or worsen during the study period, will be reported as AEs or SAEs as appropriate based on the above definitions.

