4.2.2 Investigational Treatment Periods

4.2.2.1 Period 1

Patients will be placed on supplemental oxygen consistent with standard of care.

(Group A): Nasal Reservoir plus Nasal Cannula (1 hr duration) (Group B): Nasal Cannula (1 hr duration)

- Continuous monitoring of peripheral blood oxygen saturation (by pulse oximetry) with recordings every 15 min.
- Continuous end-tidal carbon dioxide (CO₂) monitoring with recordings every 15 min.
- Record vital signs every 15 min.
- Record oxygen flow (L/min) every 15 min.
- Record concomitant medication information.
- Record adverse event information.
- Physical examination, including capillary refill time; capillary blood gases (PaO₂, PaCO₂, pH, base excess, lactate); and completion of SICK score form at end of Period 1.

4.2.2.2 Period 2

(Group A): Nasal Cannula Alone (1 hr duration)

(Group B): Nasal Reservoir and Cannula Alone (1 hr duration)

- Continuous monitoring of peripheral blood oxygen saturation (by pulse oximetry) with recordings every 15 min.
- Continuous end-tidal carbon dioxide (CO₂) monitoring with recordings every 15 min.
- Record vital signs every 15 min.
- Record oxygen flow (L/min) every 15 min.
- Physical examination, including capillary refill time; capillary blood gases (PaO₂, PaCO₂, pH, base excess, lactate); and completion of SICK score form *at end of Period* 2.

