APPENDIX A: SCHEDULE OF EVENTS

Activity	Screening	Period 0 (Baseline)	Period 1 (1 hr)	Period 2 (1 hr)
		Group A	Nasal reservoir + nasal cannula	nasal cannula
		Group B	Nasal cannula	Nasal reservoir + nasal cannula
Recruitment/Informed Consent	X			
Medical history	X			
Physical examination	X		X (end of period)	X (end of period)
Severe pneumonia (based on WHO criteria) ^a	X			
SpO ₂ 85-93% on room air (pulse oximetry)	X			
Capillary blood gas with lactate	X		X (end of period)	X (end of period)
Signs of inflammation in children that can kill (SICK) score	X		X (end of period)	X (end of period)
Hemoglobin rapid test	X			
Complete blood count (hematology panel)	X			
Malaria rapid diagnostic test	X			
Blood glucose (point of care)	X			
Comprehensive metabolic panel ^b	X			
Determine nasal reservoir size		X d		
SpO ₂ >90% on oxygen (pulse oximetry)		X		
Vital signs ^c		X f	record values every 15 min	
Record concomitant medication information		X	X	X
Continuous transdermal end-tidal CO ₂ monitoring			record values	s every 15 min
Continuous SpO ₂ monitoring (during supplemental O ₂)			record values every 15 min	
Record oxygen flow (L/min)			record values	s every 15 min
Record adverse event information			X	X

- a. Severe pneumonia based on World Health Organization criteria (Appendix B).
- b. Comprehensive metabolic panel will be obtained only if indicated as part of standard of care.
- c. Vitals signs: blood pressure, respiratory rate, heart rate, and temperature. Obtain at baseline (pretreatment) and every 15 minutes from the beginning of Period 1 through end of Period 2. Any values obtained during Screening period may be used as Baseline values.
- d. Patients with a body weight of 8-13 kg will receive treatment with a small 30 ml mask and patients with a body weight of 14-26 kg will receive treatment with a large 50 ml mask.

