APPENDIX G LABORATORY REFERENCE RANGES

iSTAT CG-	4 reportable ranges	
Lab Value	Reportable Range (units)	Lowest allowable values in data base
pН	6.5 - 8.2	6.4
BE	-30-+30mmol/L	-29
pCO ₂	5 – 130 (mm Hg)	4.9
pO ₂	5 – 800 (mm Hg)	4.9
HCO ₃	1.0 - 85.0 (mmol/L)	0.9
Total CO ₂	5 – 50 (mmol/L)	4.9
Lactate	0.30 - 20.0 (mmol/	0.2

iSTAT Chem8	+ reportable ranges	
Lab Value	Reportable Range (Conventional Units)	Lowest Values allowed in data base
Sodium	100-180(mmol/L)	
Potassium	2.0-9.0(mmol/L)	
Chloride	65-140(mmol/L)	
Ionized Calcium	0.25-2.50(mmol/L)	0,2
Glucose	1.11-38.89(mmol/L)	1.0
BUN	1.07-49.98(mmol/L)	1.0
Creatinine	17.68-1768(μmol/L)	17
Anion Gap	-10-99(mmol/L)	-9.9
Total CO2	5-50(mmolL)	4.9
Hemoglobin	3.4-25.5(g/dL)	3.3
Hematocrit	10-75(% PCV)	9.9

AReportable Ranges for the ACutrend Lactometer, Glucometer and Haemocue

Lab Value	Point of Care Equipment	Reportable Range	Lowest value in data base
Lactate	ACutrend Lactometer	0.8 -22 Mmol/L	0.7
GLYCOSE	GhucomeTER	1.1-33.3 Mars//L	1.D
HAEMOGLOBIN	HAEMOCUE 301	0-25.69/1	1.0

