If abnormal lab values are discovered during the study, the site PI will be notified and will address this issue as early as possible. Clinically significant laboratory abnormalities (see protocol Appendix F), which are new or worsen during the study period, will be recorded and reported as AEs or SAEs as appropriate based on the above definitions. Abnormal lab values will be reported as AEs only when the site PI deems them to be clinically significant. For clinically significant laboratory abnormalities, a member of the local research team (site PI, study pediatrician, or study nurse) will provide a brief report on how the abnormal value was managed.

C. Data Quality and Safety Monitoring and Review Plan

- 1. Data Quality and Management
- a. Description of Plan for Data Quality and Management— The study coordinator will review all data collection forms on an ongoing basis for data completeness and accuracy. A statement reflecting the results of the review will be sent to the sponsor at 6-month intervals. Data quality will be assessed using measures such as time from study visit to data entry, time to resolution of data queries, number of missing forms, and proportion of all study variables queried. Guidelines for concern regarding these measures are outlined below:

Measure	Goal Value	Acceptable Value
Time from visit to data entry	<1 week	<2 weeks
Time to resolution of queries	<2 weeks	<3 weeks
Percentage of missing fields on data collection forms	0	<5%

b. Frequency of Review—The frequency of data review depends according to the type of data and is summarized in the following table.

Data Type	Frequency of review	Reviewer
Subject accrual (adherence to	Every 2 weeks	Study pediatrician/coordinator and
eligibility criteria)		site PI
Protocol adherence	Monthly	Study pediatrician/coordinator and
		site PI
Adverse event rates	Monthly	Study pediatrician/coordinator and
	-	site PI
Evaluation of data relevant to	After 10 participants	Study pediatrician/coordinator,
stopping rules	have been enrolled	site PI, and UCSF PI

- 2. Subject Accrual and Protocol Adherence
- a. Measurement and reporting of subject accrual, adherence to inclusion/exclusion criteria—Review of the rate of subject accrual and adherence to inclusion/exclusion criteria will occur every 2 weeks.
- b. Measurement and reporting of protocol adherence— Data on protocol adherence will be reviewed monthly.

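### The laboratory AE rule points to the SAE form for its criteria, so no numeric criterion makes a blood gas or lactate value an AE or SAE, and the count rests on an unblinded investigator's judgment

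*Protocol*

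**What the plan says.** Section 8.1.4 states the reporting rule for laboratory results and refers out for its content: "Clinically significant laboratory abnormalities (see Appendix F". The Data and Safety Monitoring Plan (Appendix H, B.5) does the same: "Clinically significant laboratory abnormalities (see protocol Appendix F". The appendix both name is headed "Appendix F: Serious Adverse Event Reporting Form".

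The next appendix is headed "APPENDIX G LABORATORY REFERENCE RANGES". The range column of its first table is labelled "Reportable Range (units", and the companion column gives the lowest value the database accepts.

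Appendix H, B.5 then gives the working rule: "Abnormal lab values will be reported as AEs only when the site PI deems them to be clinically significant".

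The exclusion criteria in section 6.1 contain numeric limits: pCO2 above 55 mm Hg, pH below 7.20 and/or lactate above 3 mmol/L, all on room air, and SpO2 below 90% on oxygen. Section 6.2.1 (device discontinuation), section 8.1.5 and Appendix H, C.4 (withdrawal) apply when a child develops a condition that would have barred enrolment.

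For continuous CO2, section 4.2.2 writes "Continuous end-tidal carbon dioxide", while Appendix A writes "Continuous transdermal end-tidal". The synopsis, sections 4.1, 10.2.2 and 10.3, and Appendix H, C.3 use the second form.

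**The concern.** A safety rule that refers to criteria should lead to criteria, and this one leads to a blank form. Moving the pointer on one letter would not repair it, because Appendix G describes instruments, not patients.

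Section 2.3 says the device works by adding dead space, so CO2 is the safety signal a successor trial will most want from this study. Appendix H, B.4 states in advance that risks such as hypercapnia do not come from the device. With the allocation open and no written criterion, two children with the same pCO2 could be counted differently depending on which device they were wearing. Section 10.5.6 tabulates AE incidence by treatment group, and the report after 10 patients (Appendix H, D) asks whether AE rates match prior assumptions. Both would carry that subjectivity.

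The naming of the continuous CO2 measure is a smaller matter. End-tidal CO2 is a property of exhaled gas, as section 2.3 itself explains, and a transdermal reading is taken through the skin. The combined term does not tell a later reader which was recorded.

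**Working it through.** No sample size or power figure is involved. The check traces the references and compares the limits.

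1. **The pointer.** Section 8.1.4 and Appendix H, B.5 both lead to Appendix F. Its items cover event dates, category, intervention type, relatedness and action taken. It contains no laboratory threshold.

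2. **The likely intended target.** Appendix G gives, for the blood gas cartridge, pH 6.5 to 8.2, pCO2 5 to 130 mm Hg and lactate 0.30 to 20.0 mmol/L. These are measuring limits. They say what can be reported and entered, not what is abnormal.

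3. **The protocol's own limits against those ranges.** Each exclusion limit lies inside what the analyser can report: pCO2 5 < 55 < 130; pH 6.5 < 7.20 < 8.2; lactate 0.30 < 3 < 20.0. Values beyond the protocol's limits are therefore measurable.

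4. **What a crossing value does.** Under sections 6.2.1 and 8.1.5 and Appendix H, C.4, hypercapnia and acidosis are named triggers for device discontinuation or withdrawal. Lactate is reached only through the combined acidosis / lactic acidosis exclusion criterion. Section 10.5.3 then lists the child with a reason. No passage says that the same value is an AE. For that there are only the symptom-linked wording in section 8.1, which has no number, and the site PI's judgment.

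5. **Room air against oxygen.** The pCO2, pH and lactate limits are written for room air. Sections 4.2.2.1 and 4.2.2.2 place the capillary gases at the end of each treatment hour, when the child is on oxygen. The text does not say whether the limits carry over unchanged.

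6. **Whether withdrawals can stand in for a laboratory count.** With 20 children, the end-of-period samples number 20 × 2 = 40. Equal allocation gives 10 children per group. Of the 20 samples taken after a device hour, 10 (Group A) come at the end of Period 1 and 10 (Group B) at the end of Period 2, when the study finishes. For those last 10, withdrawal has almost nothing left to act on. The disposition table would therefore not count device-hour crossings evenly across the two sequences.

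7. **Size of a full listing.** 40 samples × 3 analytes = 120 values to screen. SpO2 is recorded every 15 minutes: 60 / 15 = 4 per hour, and 4 × 2 × 20 = 160 readings, or 5 × 2 × 20 = 200 if the start of each hour is also recorded.

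**The case against.** The best defence is that the safety signal does not depend on AE labels. Gases, lactate, SpO2 and continuous CO2 are named safety variables (section 10.3), and all variables are summarised descriptively (section 10.5.1). Withdrawals are listed with reasons, and AEs that lead to them are listed too. Investigator judgment is an ordinary way to call an AE, and the layout of a listing commonly belongs in an SAP. Most of this stands. It limits the defect to AE and SAE classification and makes it modest. It does not excuse a rule that cites criteria the document does not contain.

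Three stronger readings are tempting, and the documents do not support them.

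- A reader might infer that no gas or lactate value is ever flagged by rule. That is wrong: the exclusion limits operate as triggers for withdrawal and device discontinuation.
- A reader might set the Appendix G ceilings against the exclusion limits and conclude that the plan accepts extreme values as normal. Nothing in the protocol uses Appendix G to judge abnormality, and its columns are openly labelled as reportable ranges. Only the title misleads.
- A reader might infer that the continuous CO2 comparison would be an artefact of sampling exhaled gas under the reservoir. No passage describes such sampling in patients, and the exhaled-breath definition in section 2.3 belongs to the bench simulator. What remains is an inconsistent name.

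**Conclusion.** The point holds for AE and SAE reporting. Two references lead to the wrong appendix, the plausible alternative is mistitled, and no numeric criterion makes a gas or lactate result an AE or SAE. Laboratory AE counts by treatment group therefore rest on unblinded judgment. The withdrawal and discontinuation rules are a real safeguard, but they record something else and leave open how room-air limits apply to samples drawn on oxygen.

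The reach is at most 40 end-of-period samples in a descriptive feasibility study. No error rate or estimate is distorted by a calculable amount, and the measured values will still be summarised. The conclusion assumes that no laboratory limits sit in the text between Appendix C and Appendix F, which the public copy does not show. If they do, the criteria exist but both pointers are still wrong. The CO2 naming is a separate correction of wording.

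**What to change.** - Correct the reference in section 8.1.4 and in Appendix H, B.5 so that each leads to the criteria actually meant.
- Retitle Appendix G as analyser reportable ranges.
- Reconcile the laboratory AE criteria with sections 6.1, 6.2.1 and 8.1.5 and Appendix H, C.4, and state how limits worded for room air are read for samples taken on oxygen. Which limit applies clinically is for the sponsor and investigators to settle.
- List by device period every end-of-period capillary pCO2, pH and lactate, and every recorded SpO2, that crosses a limit already in the protocol, whether or not the site PI calls it an AE. This is a data listing and adds no clinical rule.
- Confirm how continuous CO2 is measured in patients, and use one name for it in the synopsis, sections 4.1, 4.2.2, 10.2.2 and 10.3, and Appendices A and H.

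The cost is text edits and one listing from data already collected: at most 120 gas and lactate values and about 160 to 200 SpO2 readings to screen. The drawback is more values to list, some of which the investigators will regard as unimportant.
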